Neurostimulation & Depression Study

Protocol Summary Document for ProofPilot Remote Studies

ProofPilot Study ID:2518

Principal Investigator

[name]

Study Purpose

Examine the safety and effectiveness of the Fisher Wallace Cranial Electrotherapy Stimulator Device on Major Depressive Disorder using two 20-minute per day treatment sessions over eight weeks.

Study Design

This is a fully remote trial where participants engage at home in the study using the ProofPilot study platform. All potential participant enrollment data, including proof of identity via government ID will be reviewed by licensed medical professionals in the participant's state prior to their full enrollment.

Participants will be randomized into an immediate or delayed treatment arm. The immediate treatment arm participants will be shipped an active Fisher Wallace device limited to Level 2 output even if a participant raises the dial beyond that. The participant will remain with the active device for the full 8 weeks.

In the delayed treatment arm, the participants will receive a sham device that looks exactly the same, but only provides treatment for 2 seconds. At week 4, sham arm participants will be unblinded and shipped an active device (limited to Level 2 output even if a participant raises the dial beyond that). The delayed arm participants will continue with active devices for the remaining 4 weeks of the trial.

Physicians, via a telemedicine visit, will diagnose participants, prescribe the device and provide medical oversight. Participants will self-report adherence and any adverse events on a daily basis through diaries. Self-report outcomes will be collected via online assessments at baseline, 2-week point, 4-week point and 8 week points. In addition, physicians will also conduct an assessment at baseline and week 4.

Weeks 1-4 of this protocol are intended to provide sufficient evidence of safety and effectiveness to support the FDA Premarket approval submission for the Fisher Wallace CES device. Data collected in weeks 5-8 of this protocol, relevant to an ongoing evaluation of safety and effectiveness, may be submitted to FDA in the form of an update report, in accordance with 21 CFR § 814.20(b)(13)(e).

Treatment Instructions

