After receiving a prescription via remote asynchronous telemedicine, the patient is randomized to either an immediate or delayed treatment arm, and delivery of the Fisher Wallace device will be made by UPS/Fedex/UPS. Upon delivery (as identified by shipment tracking code), individuals will be presented with video how-to instructions, and treatment overviews (along with some device usage troubleshooting facts). The device packaging will also include instructions. A PDF version of the instructions, along with FAQs will be made available via ProofPilot for quick reference.

Participants will be directed to use the device twice per day for 20 minutes, once soon after waking up, and the second time per day 20 minutes prior to attempting sleep.

The study timeline will commence upon completion of the first treatment as identified by the participant in ProofPilot.

Participants who have questions about the device will be referred to ProofPilot customer support. All queries will be logged and reported at the end of the study. ProofPilot will refer those questions that can not be answered with an automated frequently asked questions system to PI [name] and/or the manufacturer (Fisher Wallace) for follow-up.

Primary Outcome Measures:

- Change in Beck Depression Inventory Score in “Treatment week 4” versus Baseline in immediate versus delayed arm.

Secondary Outcome Measures:

- Change in Hamilton Depression Rating Scale from Baseline to “Treatment week 4” in immediate versus delayed arm.
- Change in Beck Depression Inventory Score in “Treatment week 2” versus Baseline in immediate versus delayed arm.
- Change in Patient Health Questionnaire - 8 (PHQ-8) score at “Treatment week 4” versus Baseline in immediate versus delayed treatment arm.
- Change in Patient Health Questionnaire - 8 (PHQ-8) score at “Treatment week 2” versus Baseline in immediate versus delayed treatment arm
- Change in Beck Depression Inventory Score from “Treatment Week 4” to “Treatment week 8” in delayed treatment arm (once they have started use of the actual device).
- Device safety, tolerability and adherence over 8 week period as measured by SAFTEE

Sample Size:

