- Fisher Wallace email marketing to patients who have not purchased a Fisher Wallace device and to providers who may refer patients to the study
- Digital advertising on GoodRx, Facebook, Instagram, Google and other common advertising platforms
- Physician referrals.

All potentially interested participants will be directed to the ProofPilot study recruitment page for registration and screening to begin the study.

Study Design/Methods

All participants upon expressing interest, will be asked to create an account on ProofPilot, and answer some basic demographic questions. (Birthdate, location, sex, timezone, preferred language).

All study activities, except those with the Fisher Wallace device itself, will be completed on ProofPilot. ProofPilot is available across any internet connected device with a reasonable screen size. No download is required.

At enrollment, the participant will be asked a series of screening questions, will complete the PHQ-8, the Beck Depression Inventory and a self administered version of the MINI.

Eligible individuals who will be self consented online, will then be asked to take a photograph with their mobile device of a government issued ID for identification. Participants will set an appointment on ProofPilot with a licensed telemedicine psychiatrist in their state within the next several days.

At that virtual visit, the physician will review the participant's responses to the MINI, and add several additional elements that require a physician assessment. Then the physician will administer the HAM-D - and make a final determination if the participant is a good for the study and authorize a prescription for the device.

Participants will then complete additional baseline measures including the QIDS-SR, PROMIS Sleep Disturbance, and Jenkins Sleep Scale. They will then enter in shipping information to place an order for the Fisher Wallace Device.

All participants will be randomized, with a 50/50 chance, into a control arm or active treatment arm. Control arm participants will receive an active treatment device at the end of week 4. This is a double blind design, the participants, nor any study staff, except those conducting fulfillment are aware of which arm the participant is in until unblinding at the end of the study.

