Eligible individuals will then be asked to take a photograph with their mobile device of a government issued ID for identification. They will then enter in shipping information to place an order for the Fisher Wallace Device.

Participants will then complete additional baseline measures including the QIDS-SR, PROMIS Sleep Disturbance, and Jenkins Sleep Scale.

Meanwhile, collected data from PHQ-8, and the Beck Depression Inventory along with proof of identification will be reviewed by medical oversight licensed in the state in which the participant resides and the order released with a prescription for the device. An appointment will be made for the physician to meet with the patient over video telemedicine. During this visit, the physician will evaluate the patient using previously collected baseline data, and their own assessments (MINI, HAM-D) to ensure proper diagnosis and set a professional assessment baseline.

Should the physician feel the participant is a good match, they will issue the prescription for the Fisher Wallace device.

Shipments will be fulfilled by the sponsor's fulfillment capacity by individuals who are not affiliated with the study. All study staff, including remote physicians, will be blinded to who receives the sham and who receives the active device. Tracking information from UPS/Fedex/USPS will trigger tasks based on where the shipment is in the fulfillment process, including at delivery.

At delivery, ProofPilot will automatically trigger instruction tasks, a treatment expectancy survey, and a notification to "Start the trial." The "Start the trial" task will trigger the 2 week, 4 week and 8 week follow up points key to the outcome measures. It will also trigger the window period for the final (week 4) participant/physician video teleconference assessment.

Participants will receive a daily treatment diary at 6:45AM (though they may complete it anytime within an 18 hour period). The daily treatment diary will ask about treatment adherence and any adverse events from the prior day and provide a morning treatment reminder. Participants will also receive an evening

treatment reminder at 7:15PM. Reminders will be presented from ProofPilot in the morning and in the evening adjusted for the participant timezone.

At the end of the study, participants will need to return both the active and sham devices to qualify for compensation.

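### The protocol promises participant blinding to the end of the study but unblinds the sham arm at week 4, when the primary outcome is due, and does not say that the ratings come first

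*Protocol*

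**What the plan says.** **Blinding.** The Study Design/Methods section describes a double-blind trial in which neither participants nor study staff, other than those handling fulfillment, "are aware of which arm the participant is in until unblinding at the end of the study". The same section separately keeps all staff, including the remote physicians, blinded to device allocation.

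**Unblinding of the sham arm.** The Study Design section states: "At week 4, sham arm participants will be unblinded and shipped an active device". It continues: "The delayed arm participants will continue with active devices for the remaining 4 weeks of the trial". Study Design/Methods puts the second device slightly differently: "Control arm participants will receive an active treatment device at the end of week 4".

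**Week-4 outcomes.** The primary outcome is the between-arm difference in BDI change from baseline to week 4. PHQ-8 and HAM-D changes at week 4 are listed as secondary. The start-of-trial "task will trigger the 2 week, 4 week and 8 week follow up points key to the outcome measures". Of the physician visit the protocol says: "It will also trigger the window period for the final (week 4) participant/physician video teleconference assessment". It gives no width for that window.

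**Use of the data.** "Weeks 1-4 of this protocol are intended to provide sufficient evidence of safety and effectiveness to support the FDA Premarket approval submission".

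**The concern.** There are two linked problems.

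1. The description of the blind is wrong as written. A participant told at week 4 that the device was a sham is not blind until the end of an eight-week study.
2. The unblinding carries the same time label as the primary endpoint, and the protocol does not order the two. BDI and PHQ-8 are the participant's own answers, and the HAM-D is rated from an interview with the participant. Knowledge of allocation can therefore affect all three, even when the physician is blinded.

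The week 1-4 comparison is the one meant to support the premarket submission. The protocol should claim only the blind that the design has, and should protect it up to the last week-4 rating. Analysis cannot restore a blind lost before the rating was made.

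**Working it through.** **Step 1: the two blinding statements.**

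| Point | Study Design/Methods | Study Design |
|---|---|---|
| Who | Participants, and staff other than fulfillment | Sham-arm participants |
| Blind ends | End of the study | Week 4 |
| Time left | None | 4 of 8 weeks |

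The first column names participants explicitly, so it cannot be read as covering staff only. For staff there is no conflict. Reading the end of the study as week 4 does not help, because the protocol also uses that phrase for the point at which both devices are returned.

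**Step 2: is the order fixed elsewhere?** Four places bear on it.

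- The secondary outcome for BDI change from week 4 to week 8 is defined "in delayed treatment arm (once they have started use of the actual device". This makes the week-4 BDI the value before active use. It does not say that the BDI precedes the unblinding notice.
- Control participants receive the active device at the end of week 4. This concerns receipt. Study Design ties unblinding to shipment, which comes before receipt, so a participant could know the allocation, not yet hold the active device, and still owe a BDI or HAM-D.
- The follow-up points run from the start-of-trial task, and the physician visit has a window of unstated width. A visit late in that window could follow the notice.
- The schedule mentions a blue bar marking device shipment and delivery. It is not legible in the text available, so any mark for the second shipment could not be read.

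The readable text orders the ratings against receipt and use of the device, but not against the notice.

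**Step 3: how much shift the design tolerates.** The documents give no bias figure, so this is a tolerance and not an estimate. Inputs from the Sample Size section: 175 in total, 1:1 (87.5 per arm, df = 173), two-sample t-test, one-sided alpha 0.025, effect 0.426 SD.

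The noncentrality for a true difference of d SD is d × √(87.5/2) = 6.614 d. The critical value of t with 173 df is 1.974. The rejection probability is P(T > 1.974), with T noncentral t.

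*The plan's own figure:* 6.614 × 0.426 = 2.818, which gives power 0.800. This matches the stated 80%.

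*Net shift s in the sham arm's week-4 mean (assumed values):*

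| s (SD) | One-sided error if s favours the device, no true effect | Power at 0.426 − s if s goes against it |
|---|---|---|
| 0 | 2.5% | 80.0% |
| 0.02 | 3.4% | 76.1% |
| 0.05 | 5.1% | 69.6% |

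Error reaches 5.0% at s = 0.0479 SD (0.0479/0.426 = 11.2% of the planned effect). Power falls to 70% at s = 0.0483 SD (0.0483/0.426 = 11.3%). Results for 87 and 88 per arm agree to three decimals.

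*Conversion to affected participants:* s is the average over the whole sham arm. If a fraction f is rated after unblinding and each shifts by b SD, then s = f × b. A net 0.048 SD needs b = 0.048/0.25 = 0.19 SD when a quarter are affected, and 0.048/0.10 = 0.48 SD when a tenth are.

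The Sample Size section frames its calculation on the PHQ-8. Carrying the standardised effect to the BDI and HAM-D is an assumption.

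**The case against.** The strongest reply accepts the contradiction but calls it a matter of wording. No between-arm efficacy outcome is listed after week 4, so the loss of blinding in weeks 5-8 damages no planned comparison. Harm to the primary comparison then rests on the unstated order, and the text leans towards ratings first: the active device comes at the end of week 4, and the week-4 BDI is the delayed arm's starting value. The unreadable schedule mark may show the order. The physicians are blinded. The tolerance figures would apply to any two-arm t-test of this size, and the shift per person must be larger if only some participants are affected.

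Much of this stands. The intent probably is ratings first, nothing shows that unblinded ratings are planned, and the figures say nothing about the likely bias. Confidence is higher on the contradiction than on the ordering gap.

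It does not remove the point. The lines that suggest an order concern the device, whereas bias would come from the notice. A blinded physician still interviews a participant who may know the allocation. Even if the schedule figure showed ratings first, the two blinding statements would conflict.

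**Conclusion.** The concern holds and should be fixed. The claim of participant blinding to the end of the study is contradicted by the planned unblinding of the sham arm at week 4, and this follows from the text alone. In addition, no readable text protects the week-4 BDI, PHQ-8 and HAM-D from being taken after that unblinding.

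The size of any bias is unknown, as is its direction. If all week-4 ratings come first, the bias from this source is nil and only the wording is wrong. If not, a net shift of roughly 11% of the planned effect would be enough to double the one-sided error or take ten points off the power. That statement assumes the planned 175 participants, the stated t-test, and a shift confined to the sham arm's mean. The severity rests on the contradiction and the missing order at the primary time point, not on these figures.

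**What to change.** - Reconcile the Study Design and Study Design/Methods sections. State that participants are blind until their week-4 BDI, PHQ-8 and HAM-D are complete, or until the week-4 visit window closes, and that weeks 5-8 are open-label. The staff blind can stay as written.
- Make the participant's unblinding notice in ProofPilot conditional on that point.
- Flag any week-4 rating made after unblinding, for a sensitivity analysis whose details can sit in the SAP.
- Reconcile the two descriptions of second-device timing with this order. That timing is for the sponsor to settle, and none is proposed here.

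**Cost.** Protocol wording and one platform condition. The downside is a later notice for participants whose week-4 visit is late. Because the 8-week point is counted from the start-of-trial task, their active period could fall short of the four weeks described, with less exposure behind the week-4-to-8 BDI outcome. How much shorter cannot be stated, because the protocol gives no window width.

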Participants will complete the COMBINE SAFTEE at the 2 week, 4 week and 8 week mark to provide additional data for safety and tolerability not otherwise collected.

All adverse events will be followed up upon and tracked in ProofPilot.

Participant Compensation

Participants may earn up to \$100 for participation in the study.

- \$10 Visa Gift Card for Baseline through completing first Fisher Wallace Treatment (aka 'Start Task') as identified above..
- \$90 presented within 2 weeks of study completion (as defined by return of both the active and shame devices) based on the following:
 - \$20 for each 2 week check in (up to \$60)
 - Up to \$30 as calculated by percentage of daily diaries completed over the 8 weeks

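### The device-return rule cannot be met by the immediate arm as written, and it implies that the delayed arm keeps a look-alike sham beside the active unit in weeks 5-8

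*Protocol*

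**What the plan says.** **Devices by arm (Protocol, Study Design).** For the immediate arm: "The immediate treatment arm participants will be shipped an active Fisher Wallace device limited to Level 2 output", and "The participant will remain with the active device for the full 8 weeks". Nowhere is a sham sent to this arm. For the delayed arm: "the participants will receive a sham device that looks exactly the same, but only provides treatment for 2 seconds". Then: "At week 4, sham arm participants will be unblinded and shipped an active device", and "The delayed arm participants will continue with active devices for the remaining 4 weeks of the trial".

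**Return rule (Protocol, Study Design/Methods).** "At the end of the study, participants will need to return both the active and sham devices to qualify for compensation". The sentence addresses participants in general, with no distinction by arm. No other text asks for the sham back at week 4, or says that it is disabled, relabelled or exchanged.

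**Payment (Protocol, Participant Compensation).** $10 is paid for the period up to the first treatment. The other $90 follows study completion, glossed as "as defined by return of both the active and shame devices", again without an arm qualifier.

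**Recording of use.** Study Design and Study Design/Methods describe a daily self-report diary covering the previous day's use and adverse events. They do not say that it records which unit was used.

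**The concern.** There are two linked problems, and the first is the firmer one.

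1. The return rule does not fit the design. It asks every participant for two devices, while one arm is sent only one.

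2. Because the rule names the sham among the devices handed back when the study ends, it implies that the sham is still in the home until then. For four weeks a delayed-arm participant would then have two units of the same appearance, one of which delivers essentially no treatment. A session run on the wrong unit would be logged as active use, and nothing described would allow it to be identified later.

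At stake are the secondary outcome on Beck change from week 4 to week 8 in the delayed arm, which presupposes use of the real device, and that arm's share of the week 5-8 safety and adherence data. Sham sessions counted as active would weaken the apparent effect, understate adverse events per active session and overstate active adherence. Study Design says that the week 5-8 data may go to FDA as an update, so clean exposure records have some value.

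**Working it through.** **Step 1. The plan's only power figure.** Inputs from Sample Size: effect size 0.426, one-sided alpha 0.025, power 80%, 1:1 allocation, 175 in total.

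n per arm = 2 × (1.960 + 0.842)² / 0.426² = 2 × 7.85 / 0.1815 ≈ 86.5, rounded up to 87, or 174 in total.

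With 87 + 88 participants, the noncentral t gives power of 80.0%. The stated figure reproduces. This point does not depend on it; it supplies only the arm size, 175 / 2 = 87.5.

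**Step 2. Device flow against the return rule.**

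| | Immediate arm | Delayed arm |
|---|---|---|
| Weeks 1-4 | 1 active | 1 sham |
| Shipped at week 4 | nothing | 1 active |
| Held in weeks 5-8 | 1 active | 1 sham + 1 active, same appearance |
| Rule asks for | active and sham | active and sham |
| Can comply as worded | no | yes |

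**Step 3. Payment.** $10 + $90 = $100, and the $90 is $60 for check-ins plus $30 for diaries. All $90 waits on the return. Applied literally, the immediate arm is limited to $10.

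**Step 4. Which outcomes are exposed.**

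- Beck and PHQ-8 at weeks 2 and 4, and the Hamilton scale at week 4, compare the arms on their first devices. They precede the two-device period.
- The delayed arm's Beck change from week 4 to week 8 falls inside it.
- The 8-week safety and adherence outcome is exposed for the delayed arm in weeks 5-8 only. The immediate arm holds a single active unit throughout.

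**Step 5. Scale of the exposed period.** Two sessions a day over 28 days gives at most 2 × 28 = 56 sessions per delayed-arm participant. The active unit is only shipped at week 4, whereas the week-8 assessment is timed from the start-of-trial task. Each day before first active use therefore removes 2 / 56 = 3.6% of the planned active sessions. The documents give neither a transit time nor a mix-up rate, so the calculation stops here.

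**The case against.** The strongest case against has four parts.

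- **Unblinding.** Delayed-arm participants are told at week 4 that their first unit was a sham, and have every reason to use the new one. This stands as a reason to expect few mix-ups. It does not make two identical units distinguishable once both are unpacked. The Protocol also conflicts with itself here: Study Design/Methods places unblinding at the end of the study. If that text were followed, the safeguard would be gone.
- **Silence in a summary document.** Labels or serial numbers may exist in materials that are not shown. That is possible, so the claim is limited to what is described. That the sham stays in the home is not inferred from silence alone, because the rule lists it among the end-of-study returns.
- **Intended meaning.** The sponsor very probably meant that participants return whatever they were sent. That is likely, but the unqualified wording appears twice and controls most of the payment.
- **Limited consequence.** The exposed efficacy outcome is an unblinded change within one arm, with no concurrent sham, and stray sham sessions would make it more conservative. This is fair for efficacy. It does not carry over to safety, where lower recorded event rates are not conservative, or to adherence.

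A reader might infer that the whole immediate arm fails to complete the trial, or that the incentive to reach week 8 differs by arm. The documents do not support this. Completion in Participant Compensation only releases a payment; no text uses it to define completers or an analysis set, and nothing shows how the rule is put to participants.

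**Conclusion.** The point holds in a limited form. As worded, the return rule cannot be met by the immediate arm, 87 or 88 of 175 participants, and for them $90 of the $100 depends on it. This is a contradiction in the text about payment. It does not define an analysis population.

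The rule also implies that the delayed arm holds two look-alike units in weeks 5-8. A mix-up is possible and, with the recording described, could not be traced. This rests on two assumptions: that the sham is not retrieved or marked under some instruction not shown, and that the diary does not identify the unit.

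It is tempting to attach a dilution figure, for instance a 5-20% loss of effect if 5-20% of sessions run on the sham. Under proportionality that only returns the assumed input. The documents contain nothing to anchor the rate, so the bias cannot be estimated.

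Nor does the point reach the primary result. The week-4 comparison, the other week-2 and week-4 between-arm comparisons and the power calculation are unaffected. The correction is worth making because it is cheap and the lost information could not be recovered afterwards.

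**What to change.** 1. **Wording.** In Study Design/Methods and Participant Compensation, make payment depend on return of each device that the participant was sent: one in the immediate arm, two in the delayed arm.
2. **Sham retrieval.** Have the delayed arm return the sham in a prepaid mailer when the active device is delivered, once the week-4 assessments are complete. Fulfilment personnel should handle it, so that study staff and physicians stay blinded, in particular until the week-4 Hamilton rating, which has its own window.
3. **Exposure record.** Add to the ProofPilot diary the label or serial number of the unit in use and the date of first use of the active device. Keep these entries out of sight of anyone who is still to be blinded. The start date also separates the sham-only days while the active unit is in transit.
4. **No gating.** Do not withhold any diary, adverse-event or outcome task until the return is confirmed. Doing so could lose safety and adherence data in one arm only.

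The two statements on when the delayed arm is unblinded should be reconciled in the same edit.

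Cost: two sentences of protocol text, an earlier return shipment for a device that must come back anyway, and a short addition to the diary.

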Sample size for the study is based on the primary outcome measure of PHQ-8. The difference between the randomized treatment control subjects for the change in score from “Treatment Week 4” versus baseline will be compared with a two-sample t-test at the one-sided 0.025 alpha level. For a planned sample size of 175 total subjects with 1:1 allocation, the study will provide 80% power for an effect size of 0.426 where effect size is based on the ratio of the difference of means over the standard deviation.

p value: two-sample t-test at the one-sided 0.025 alpha level

Statistical Analyses:

Primary analyses of primary and secondary outcome measures will be based on the comparison of the randomized groups via t-tests for means for the change from baseline. Sensitivity analyses for the assumption of normality and for the impact of missing data will be performed. Subgroups results based on sex and race will be provided.

Inclusion/Exclusion

- Age greater than or equal to 21
- US resident
- Can receive packages to their home via UPS/Fedex/USPS
- Major Depressive Disorder
- PHQ-8 Score greater than 10 (show some signs of mild to moderate depression)
- PHQ-8 Score less than 20 (given remote study serious depressed should be excluded)
- Read/write English
- have not contemplated suicide in the past year
- not been institutionalized for mental health issues.
- not currently experiencing problems with alcohol or drug abuse
- can commit to not drinking alcohol 4 hours before bedtime for the duration of the study
- can commit to two (2) 20 minute sessions per day for 8 weeks
- has not used a brain stimulation treatment in one year
- no suspected or known history of heart disease
- no pacemaker
- not under medical supervision for other serious medical condition
- not taking opioids
- are a resident of states in which we have licensed medical professionals
- Any co occurring significant psychiatric disorder that would impair participant's participation
- any use of illicit drugs

Those with a PHQ-8 score greater than 20 will be directed to contact local mental health assistance and will be provided with the National Suicide Prevention Hotline number for immediate assistance.

Recruitment

Individuals in the study will be recruited in two forms targeted to the states in which we have contracted with licensed medical professionals.

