- **Promis Sleep Disturbance:** The PROMIS-SD had greater measurement precision than the Pittsburgh Sleep Quality Index (PSQI) and the Epworth Sleepiness Scale (ESS) as indicated by larger test information values across the continuum of severity, despite having fewer total items, a major advantage for both research and clinical settings.³
- **COMBINE SAFTEE** (systematic assessment for treatment of emergent events modified for mental health and substance abuse)

The blue bar indicates shipment/delivery of the active or sham device.

¹ Kroenke, Kurt; Spitzer, Robert L; Williams, Janet B W (2017-05-31). "The PHQ-9". Journal of General Internal Medicine. 16 (9): 606–613. doi:10.1046/j.1525-1497.2001.016009606.x. ISSN 0884-8734. PMC 1495268. PMID 11556941

² Löwe, Burnd; Spitzer; Gräfe; Kroenke; Quenter; Zipfel; Buchholz; Witte; Herzog (February 2004). "Comparative validity of three screening questionnaires for DSM-IV depressive disorders and physicians' diagnoses". Journal of Affective Disorders. 78 (2): 131–140. doi:10.1016/s0165-0327(02)00237-9. PMID 14706723.

³ A. John Rush, Ira H. Bernstein Development of short forms from the PROMISTM sleep disturbance and Sleep-Related Impairment item banks, Behav Sleep Med. 2011 Dec 28; 10(1): 6–24. doi: 10.1080/15402002.2012.636266 PMCID: PMC3261577 NIHMSID: NIHMS335121 PMID: 22250775

	Enroll	Baseline		2-Week	4-Week	8 Week
Inclusion/Exclusion	X					
Consent						
PHQ-8	X			X	X	X
Beck Depression Inventory	X			X	X	X
M.I.N.I Screen	X					
HAM-D	X				X	
Physician Telemedicine Visit	X				X	
Randomization	X					
Treatment Expectancy			X			
Instructions			X			
Quick Inventory of Depressive Symptomatology (QIDS-SR)		X		X	X	X
Jenkins Sleep Scale		X			X	X
Promis Sleep Disturbance		X		X	X	X
COMBINE SAFTEE				X	X	X
Final Feedback & Tolerability						X
Daily treatment adherence and adverse events						

Adverse Event Reporting & Medical Oversight

Licensed medical providers in the state in which the participant lives will provide medical oversight for this effort.

Adverse events will be collected qualitatively via customer support in the ProofPilot platform. In addition, medical oversight staff will automatically receive alerts if participants have a PHQ-8 score over 20 at the 2 week, 4 week or 8 week point. Those participants will also receive notifications to contact local medical support.

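### The only automatic follow-up alert is a PHQ-8 total over 20; no follow-up trigger is specific to suicidal ideation, although past-year ideation bars entry to this fully remote trial

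*Protocol*

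**What the plan says.** Study Design in the protocol describes a fully remote trial, with participants at home and using an online platform.

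Inclusion/Exclusion admits PHQ-8 scores above 10 and below 20. As a separate criterion, it requires that participants "have not contemplated suicide in the past year". People who score above 20 at screening are referred to local mental health assistance and "will be provided with the National Suicide Prevention Hotline number for immediate assistance".

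For follow-up, Adverse Event Reporting & Medical Oversight states one automatic rule: "medical oversight staff will automatically receive alerts if participants have a PHQ-8 score over 20" at the 2, 4 or 8 week point. On the participant's side, "Those participants will also receive notifications to contact local medical support".

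The same section gives two further routes: "Adverse events will be collected qualitatively via customer support in the ProofPilot platform", and "Participants will complete the COMBINE SAFTEE at the 2 week, 4 week and 8 week mark". It adds a general undertaking to follow up and track every adverse event. Study Design/Methods adds a daily diary that asks about adverse events on the previous day. The schedule of assessments has a physician telemedicine visit and a HAM-D at week 4.

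**The concern.** At entry the protocol treats suicidal ideation as a risk in its own right, listed separately from the PHQ-8 limits. In follow-up, the only rule that alerts a clinician automatically uses the PHQ-8 total, and ideation is not mentioned again. Followed exactly, that rule is silent for a participant with new ideation whose total is 20 or below.

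What is at stake is participant safety, in both arms. Participants are at home, and the only scheduled physician contact after baseline is at week 4. The existing routes depend on what the participant reports in the diary, on SAFTEE or to customer support. The text does not say that such a report alerts a clinician automatically.

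**Working it through.** The protocol gives no figure on this point to reproduce. The check is a comparison of the entry rule, the alert rule and the other follow-up routes.

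**1. What the alert responds to.** It is a threshold on the total score, not on any single answer. It is therefore not specific to ideation, whichever items the PHQ-8 form contains and wherever the threshold is set.

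**2. Where the threshold lies relative to entry.**
- Inputs: entry above 10 and below 20 (Inclusion/Exclusion); alert over 20 (Adverse Event Reporting & Medical Oversight).
- In whole points, entry totals run from 11 to 19 and the lowest alerting total is 21.
- Rise needed = 21 − entry total. From 11: 21 − 11 = 10. From 15: 21 − 15 = 6. From 19: 21 − 19 = 2.

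This is context only. It shows that a participant whose total is unchanged from entry never triggers the alert. It does not measure the ideation gap, for the reason in step 1.

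**3. What else could detect new ideation.**

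| Route | When | Automatic alert stated | Ideation mentioned |
|---|---|---|---|
| PHQ-8 total | Weeks 2, 4, 8 | Yes, over 20 | No |
| Daily diary | Daily | No | No |
| Customer support | When the participant makes contact | No | No |
| COMBINE SAFTEE | Weeks 2, 4, 8 | No | No |
| BDI and QIDS-SR | Weeks 2, 4, 8 | No | Items not listed |
| Physician visit with HAM-D | Week 4 | Not needed, a clinician is present | No |

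The undertaking to follow up all adverse events is the response to what these routes collect, not another means of detection. Week 8 also has a final feedback and tolerability form, with no alert attached. The MINI appears among the measures described as repeated, but the schedule shows it at enrolment only. Even if it were repeated, no alert is tied to it.

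**4. Result by time point, for new ideation with a total of 20 or below.**
- Week 2: no automatic alert; the diary, SAFTEE and customer support remain.
- Week 4: no automatic alert, but a physician sees the participant and rates the HAM-D.
- Week 8: as week 2, with no scheduled physician visit.
- Between assessments: the diary and customer support only.

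**The case against.** The strongest reply is that the protocol already provides for this. New ideation in a depression trial would ordinarily count as an adverse event. The diary asks about adverse events every day, SAFTEE asks at three time points, and every adverse event is to be followed up. At week 4 a clinician is present, so an automatic alert adds little. Excluding people with past-year ideation also lowers the risk in those enrolled. All of this stands, and it narrows the point to the lack of an automatic trigger specific to ideation.

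It does not remove the point. The diary and SAFTEE collect answers, but nothing in the text sends such an answer to a clinician automatically, whereas the protocol does this for the PHQ-8 total.

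A second reply is that the document calls itself a protocol summary, so operational detail may sit elsewhere. That is fair for who acts on an alert and how soon. Those are matters of missing detail and form no part of this finding. But the document has its own section on adverse events and oversight, fixes an alert rule there and refers to no separate safety plan. If such a plan exists and covers ideation, a cross-reference would settle the matter.

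**Conclusion.** The point holds in limited form. The only automatic alert stated for follow-up is a PHQ-8 total over 20, no follow-up trigger is specific to suicidal ideation, and new ideation with a total of 20 or below raises no automatic alert. It should be corrected because safety is at stake and the remedy is cheap.

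The practical gap is mainly at weeks 2 and 8. Its size in participants is unknown: the protocol gives no rate of ideation, and the 175 planned participants are those the rule covers, not those who would be missed.

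A reader might infer three stronger things that the document does not support:
- *That ideation would go undetected or unfollowed.* General routes exist and may well find it.
- *That the rise of 2 to 10 points shows the threshold to be wrong.* No threshold on a total is specific to ideation, and this one matches the score above which people are referred at screening.
- *That the entry rule and the alert rule contradict each other.* One selects who enters and the other monitors them; they can both hold.

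The finding does not depend on which items any scale contains. Only the remedy does.

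**What to change.** Keep the PHQ-8 alert. Add an automatic alert to medical oversight when a suicidality item on a self-report scale already collected at weeks 2, 4 and 8 is endorsed, at a level that medical oversight sets. This assumes that the BDI or the QIDS-SR has such an item, which should be confirmed from the sponsor's forms because the protocol does not list the items. If neither has one, add one direct question on suicidal thoughts to the same online assessments. Send the hotline number already used at screening to anyone who triggers either alert.

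The cost is one more trigger in the existing platform and a short protocol addition, plus one question at three time points if the assumption fails. Existing oversight staff would receive some extra alerts, including false positives. No visit is added, and the sample size and analysis do not change. The gain is mainly at weeks 2 and 8, since a physician already sees participants at week 4. The change adds no check between the scheduled assessments, where the daily diary remains the main route.
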